Attachment Materials for Intervention Churches R01 Version 1 Dated 3.18.2015_Part3

Document Name Materials for Intervention Churches R01 Version 1 Dated 3.18.2015_Part3

Document Type **Other Documentation**
Attachment [name] CITI Biomedical Investigator training certificate

Document Name [name] CITI Biomedical Investigator training certificate

Document Type **Other Documentation**

Attachment [name] CITI
Document Name [name] CITI

Document Type **Other Documentation**
Attachment CITI Completion Report [name]
Document Name CITI Completion Report [name]

Document Type **Other Documentation**
Attachment Letters of Support
2.Palestine.NewBethel.ChristFellow.Canaan.Friends
hip.GBHS.MetroSpir.VictLife.Dated 6.19.2015
Document Name Letters of Support
2.Palestine.NewBethel.ChristFellow.Canaan.Friends
hip.GBHS.MetroSpir.VictLife.Dated 6.19.2015

Document Type **Other Documentation**

Protocol Title: Assessing an HIV Education and Screening Intervention in African American Churches

Protocol Type: Expedited/Full Board Application

Date Submitted: 11/21/2017

Approval Period: 12/05/2017-12/04/2018

Important Note: This Print View may not reflect all comments and contingencies for approval. Please check the comments section of the online protocol. Questions that appear to not have been answered may not have been required for this submission. Please see the system application for more details.

Attachment Health Beliefs and Behaviors 6 month amendment
Version 1 dated 2-2-2016

Document Name Health Beliefs and Behaviors 6 month amendment
Version 1 dated 2-2-2016

Document Type **Other Documentation**
Attachment Sunlight Missionary Baptist Church Signed MOA
Wave 2

Document Name Sunlight Missionary Baptist Church Signed MOA
Wave 2

Document Type **Other Documentation**
Attachment Glory Bible Fellowship and Destiny Life Center MOA
Document Name Glory Bible Fellowship and Destiny Life Center MOA

Document Type **Other Documentation**
Attachment Paseo Baptist Church signed [name] MOA W2
Document Name Paseo Baptist Church signed [name] MOA W2

Document Type **Other Documentation**
Attachment Swope Parkway United Christian Church MOA W2
Document Name Swope Parkway United Christian Church MOA W2

Document Type **Other Documentation**
Attachment Calvary Temple Baptist Church MOA Wv2
Document Name Calvary Temple Baptist Church MOA Wv2

Document Type **Other Documentation**
Attachment Kingdom Word Ministries MOA Wv2
Document Name Kingdom Word Ministries MOA Wv2

Protocol Title: Assessing an HIV Education and Screening Intervention in African American Churches
Protocol Type: Expedited/Full Board Application
Date Submitted: 11/21/2017
Approval Period: 12/05/2017-12/04/2018
Important Note: This Print View may not reflect all comments and contingencies for approval. Please check the comments section of the online protocol. Questions that appear to not have been answered may not have been required for this submission. Please see the system application for more details.

Document Type Attachment Document Name
	
Other Documentation Memorial Missionary Baptist Church MOA W2 Memorial Missionary Baptist Church MOA W2

Document Type Attachment Document Name
	
Other Documentation United Believers Community Church MOA Wv2 United Believers Community Church MOA Wv2

Document Type Attachment Document Name
	
Other Documentation Good Samaritan Baptist Church MOA Wv2 Good Samaritan Baptist Church MOA Wv2

Document Type Attachment Document Name
	
Other Documentation Health Beliefs and Behaviors 12 month Version 1 Dated 8-2-2016 Health Beliefs and Behaviors 12 month Version 1 Dated 8-2-2016

Document Type Attachment Document Name
	
Other Documentation Informed Consent Form Amend R01 APPENDIX B HBB Survey Version 5 Clean Copy Dated 2-10-2016_Aproved12.05.16 Informed Consent Form Amend R01 APPENDIX B HBB Survey Version 5 Clean Copy Dated 2-10-2016_Aproved12.05.16

Document Type Attachment Document Name
	
Other Documentation Focus Group Discussion Guide Version 1 Dated 4.12.17 Focus Group Discussion Guide Version 1 Dated 4.12.17

Document Type
	
Other Documentation

Protocol Title: Assessing an HIV Education and Screening Intervention in African American Churches

Protocol Type: Expedited/Full Board Application

Date Submitted: 11/21/2017

Approval Period: 12/05/2017-12/04/2018

Important Note: This Print View may not reflect all comments and contingencies for approval. Please check the comments section of the online protocol. Questions that appear to not have been answered may not have been required for this submission. Please see the system application for more details.

Attachment	Focus Group Survey Version 1 Dated 4.14.17
Document Name	Focus Group Survey Version 1 Dated 4.14.17

Document Type	Other Documentation
Attachment	Informed Consent Form Amend R01 APPENDIX B HBB Survey Version 5 Clean Copy Dated 2-10-2016_Approved
Document Name	Informed Consent Form Amend R01 APPENDIX B HBB Survey Version 5 Clean Copy Dated 2-10-2016_Approved

Statistical Analysis Plan Cover Page

Official Study Title: Assessing HIV Screening in African American Churches
NCT02529644

Latest IRB approval date: 12/5/2017

Date created: May 7, 2013

Note: No updates were made since date created

Statistical Analysis Plan

Specific Aim 1. Test a religiously/culturally-tailored, eTPB church-based HIV screening intervention against a standard information condition and a waitlist control condition on receipt of HIV screening and HIV sexual risk behaviors among an AA church-population at 6 and 12 months. Hypothesis. The religiously/culturally-tailored, eTPB church-based HIV screening intervention will evidence higher HIV screening rates and lower sexual risk behaviors than the standard information and waitlist control conditions.

Data will be initially summarized using means, standard deviations, and percentages. Our primary outcome is receipt of HIV testing (tested vs. not-tested) at 12 months. We'll also examine outcomes at 6 months. Churches are the unit of randomization and participants nested in churches will be the level of analysis. Therefore, differences between intervention and standard information groups will be analyzed using random effects logistic regression to account for the clusters and the pairing, or matching, of churches. Multilevel, multivariate models will include fixed-effect terms for experimental condition and potential mediators and moderators, as well as random effect terms for church nested in treatment condition and individual nested within church. This approach has been widely used in other church-based studies. Adjusted odds ratios for HIV testing (and confidence intervals) will be computed for mediators/moderators. Other covariates will be added as indicated by univariate analyses conducted on baseline data. A propensity score matched analysis will also be run using all available covariates. We will use R and SAS statistical software generalized estimating equations and generalized linear mixed modeling for data analyses to determine if there is a difference in HIV screening rates over time between intervention and standard information groups with/without adjusting for covariates. We will do a stratified analysis by Wave to explore differences between: a) Wave 1 intervention and waitlist groups and b) Wave 1 standard information and waitlist groups using similar analysis methods described above. A similar process will also be used to analyze HIV sexual risk behaviors using mixed-model ANOVA programs that allows for adjustment of participant nonindependence within churches.

Specific Aim 2. Evaluate the role of potential mediators and moderators associated with HIV screening behaviors among a church-population at 6 and 12 months.

Mediation analyses will examine to what extent possible intervention effects on HIV testing might be explained by potential mediators, including TPB-based variables (attitude, normative beliefs, behavioral control, intentions) and other covariates (HIV stigma, HIV knowledge, intervention exposure). We will assess if: 1) intervention is significantly related to outcome (HIV testing); 2) intervention is significantly related to potential mediators; 3) mediators are significantly related to outcome. Specifically, we will estimate the indirect effects defined in terms of products of path coefficients—linking the intervention to outcomes via each potential mediating variable using multilevel structural equation modeling. The statistical significance and precision of these indirect effects will be addressed by: a) employing the product of coefficients approach and b) obtaining bootstrapped confidence intervals for indirect effects. Mediation will be tested using the Sobel test available as a SAS macro and an R package, *bstats*, and by using structural equation models in MPLUS software as described by MacKinnon et al. Effects of potential moderators' ability to modify the strength/direction of the potential causal relationship will be tested using interaction tests in a multifactorial model.

Specific Aim 3. Conduct a process evaluation to understand study implementation facilitators, barriers, fidelity, and costs and examine relationships between study implementation, intervention dose and exposure, and intervention outcomes to identify and improve essential intervention components.

Implementation dose and fidelity. Direct observation fidelity checklist and online documentation data will be analyzed using means, standard deviations, and percentages to assess study group dose and fidelity. **Intervention program costs** will be assessed overall and per participant using summation of implicit costs (e.g., volunteer time, church in-kind) tracked with the online documentation system and explicit costs (e.g., provision of training/technical assistance, HIV Tool Kit costs). **Focus group discussions** will be audio-recorded, transcribed, coded, and analyzed using NVivo, a qualitative data software program. Coding protocols will include initial transcription "open-coding" (e.g., identifying key words, themes, behavioral descriptions), category grouping (e.g., church-based testing barriers), and code map development to further categorize and retrieve factors (e.g., challenges, facilitators) related to delivery/receipt of church-based HIV testing services and intervention refinement strategies/tools. Intercoder agreement will be assessed with the kappa coefficient.

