Data collection. Data collection for this study consists of recruited Wave 1 participants completing a Health Beliefs and Behaviors survey assessment at baseline, 6 months, and 12 months. Wave 2 participants will complete the survey four times: baseline 1, baseline 2 (6 months), 12 months, and 18th months. The Health Beliefs and Behaviors survey instrument (see Attachment) was developed by the research team led by [name] and tested for reliability/validity in the TIPS pilot study. The survey inquires

Protocol Title: Assessing an HIV Education and Screening Intervention in African American Churches

Protocol Type: Expedited/Full Board Application

Date Submitted: 11/21/2017

Approval Period: 12/05/2017-12/04/2018

Important Note: This Print View may not reflect all comments and contingencies for approval. Please check the comments section of the online protocol. Questions that appear to not have been answered may not have been required for this submission. Please see the system application for more details.

participants about history of HIV/STD screening, facilitators/barriers to HIV screening, beliefs/social norms related to screening, risky behaviors associated with HIV/STDs, and exposure/satisfaction with study activities. Data collection procedures use the survey follow below.

1. Each participating church pastor will introduce the study PI (or research study coordinators) during the designated church service (e.g., Sunday morning or midweek service) and church community outreach event, which will be determined by each participating church's pastor and leadership. The study PI (or research study coordinator) will then review the scripted consent form information (See Appendix A) during the church service with church members and during the church outreach event with community members.
2. After the church services and church community outreach events, the research team will then review the informed consent script (See Appendix A) with willing adult members in the church's fellowship hall or large meeting room. The informed consent script will be used as a screening tool to identify eligible participants.

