3. Once eligible volunteering participants have been identified, the research team member will review the informed consent form with the participant (See Appendix B). The form will include information about the study, the time commitment and reimbursement for participation, and how the survey information will be handled. The form will also inform the participant that their participation is confidential and completely voluntary. Additionally, the form will review the minimal risks for participating and PI and SSIRB contact information. They will be instructed to not include any personal identifiers on the survey and other survey materials.
4. If volunteering participants choose to participate in the survey data collection after the consent process, they will be given: a) the Health Beliefs and Behaviors Survey (used in our previous study Protocol 016008; See Attachment) to be completed in the church's fellowship hall or large meeting room at that time (they will be assured of ample room for privacy/confidentiality in completing the survey); and b) an unmarked manila envelope. The first section of the survey instructs participants to create their own study number (secret code) via a series of questions (e.g., first letter of your mother's first name). The survey includes questions regarding: their opinions on African American health screening behaviors (including HIV/STD screening) and preventive behaviors (e.g., exercise, not smoking, healthy eating), HIV/STD health risk behaviors, and beliefs about HIV/STDs. The survey also asks about religious activities, beliefs and knowledge about HIV/STDs, opinions on whether their church should be involved in HIV/STD-related activities and participant exposure to these activities, opinions about drug users and homosexuality, and their demographic information. Participants will also be asked about exposure and satisfaction to their relevant study treatment arm in surveys subsequent to baseline survey(s).
5. Upon completion of the survey, the participants will be asked to place the survey in the envelope and seal it. They will then be asked to place the sealed envelope in a large sealed box to further ensure anonymity. They will then be given the designated and thanked for completing the survey.

Feasibility/Program Evaluation Data Collected from Church Health Liaisons (CHL):

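### The Aim 1 models put potential mediators beside condition, and no mediator-free model is designated as the primary 12-month analysis

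*SAP*

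**What the plan says.** The SAP, under Specific Aim 1, makes tested versus not tested at 12 months the primary outcome. It then says that "differences between intervention and standard information groups will be analyzed using random effects logistic regression", accounting for clusters and pairing. The next sentence reads "Multilevel, multivariate models will include fixed-effect terms for experimental condition and potential mediators and moderators", with random effects for church and for individual. The only odds ratios promised are these: "Adjusted odds ratios for HIV testing (and confidence intervals) will be computed for mediators/moderators". Protocol 4i carries the same sentences.

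Both documents add covariates picked from univariate analyses of baseline data, and a propensity-matched analysis on all available covariates. The SAP alone adds that GEE and mixed models will determine "if there is a difference in HIV screening rates over time between intervention and standard information groups with/without adjusting for covariates". None of these analyses is labelled primary.

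SAP Specific Aim 2 lists the potential mediators: four theory-based variables (attitude, normative beliefs, behavioural control, intentions) and "other covariates (HIV stigma, HIV knowledge, intervention exposure"). Its first step tests arm against outcome. Protocol 4a, data collection step 4, says of the timing: "Participants will also be asked about exposure and satisfaction to their relevant study treatment arm in surveys subsequent to baseline survey(s"). Protocol 4a also says that the survey asks "participants about history of HIV/STD screening", but baseline testing is not a stated model term.

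**The concern.** Protocol 2a asks whether TIPS raises testing rates compared with standard information. That is a total-effect question. A mediator carries part of that effect, so once it is in the model the coefficient for condition describes only what is left after the mediator is held fixed. That coefficient can be attenuated, and it can also be biased if something unmeasured drives both mediator and testing.

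The sentence that brings mediators in stands under Aim 1, directly after the sentence naming the arm comparison. Aim 2 calls stigma, knowledge and exposure covariates, and Aim 1 plans covariate-adjusted runs. An analyst could follow the text literally and report a mediator-adjusted arm coefficient as the main result, or could choose between models after seeing the data.

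**Working it through.** **What the passages settle**

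| Question | Answer in the documents |
|---|---|
| Model family for the arm comparison | Random effects logistic regression (SAP Aim 1; Protocol 4i) |
| Mediators in the multilevel models? | Yes, as fixed effects beside condition (same places) |
| Any listed mediator certainly post-baseline? | Intervention exposure (SAP Aim 2 with Protocol 4a) |
| The other six? | Not stated which measurement enters; the survey in Protocol 4a already covers HIV beliefs and knowledge |
| Mediator-free comparisons present? | Yes: the regression sentence names no mediators; a run without covariates (SAP only); Aim 2 step 1 |
| One of them designated primary? | No |

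**Illustration of size.** The documents give no mediator strength, shift or correlation, so those inputs are assumptions. The pilot's 12-month rates (Protocol 3a) are 59% and 41%: a difference of 18.0 points and a crude odds ratio of (0.59/0.41)/(0.41/0.59) = 2.07, close to the reported 2.04.

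Odds ratios are a poor yardstick here because conditioning alone moves them. With zero mediation the arm odds ratio goes from 2.07 to between 2.10 and 2.36 (one mediator) or 2.12 and 2.70 (seven). The comparison is therefore in percentage points.

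One mediator: M ~ N(0,1) in controls and N(d,1) under TIPS, with logit P = a_arm + b·M. The two intercepts are solved by Gauss-Hermite quadrature so that the marginal rates are 41% and 59%. The direct part is E[expit(a1 + b·M0)] − 41%, where M0 is the control distribution.

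Example with odds ratio 2 per SD (b = 0.693) and d = 0.5: a0 = −0.403, a1 = 0.057, and the direct part is 51.3% − 41% = 10.3 points.

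| Shift d (SD) | OR 1.3 | OR 1.5 | OR 2 | OR 2.5 |
|---|---|---|---|---|
| 0 | 18.0 | 18.0 | 18.0 | 18.0 |
| 0.2 | 16.7 | 16.1 | 14.9 | 14.2 |
| 0.5 | 14.8 | 13.2 | 10.3 | 8.4 |
| 0.8 | 12.9 | 10.3 | 5.6 | 2.6 |

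Seven mediators with common correlation ρ and equal shifts d reduce to one composite: f = √(7 + 42ρ), slope b·f, shift 7d/f. For odds ratio 1.2 each, ρ = 0.3 and d = 0.2: f = √19.6 = 4.43, slope 0.182 × 4.43 = 0.81, shift 1.4/4.43 = 0.32, direct part 12.5 points. Over odds ratios 1.1 to 1.3 and ρ 0.2 to 0.5 the direct part is 14.3–16.5 points at d = 0.1, 10.6–14.9 at 0.2 and 6.8–13.4 at 0.3.

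**Power of the arm test.** This was simulated with 600 runs, 14 churches of 65 participants, church SD 0.2 on the logit scale (assumed), matching ignored, cluster-robust errors and t with 12 df. Without mediators, power is 98.5%. With seven mediators (odds ratio 1.2 each, ρ = 0.3) it is 99.2%, 96.0%, 85.2% and 64.2% at d = 0, 0.1, 0.2 and 0.3. A repeat with 400 runs gave 99%, 97%, 86% and 69%. The levels depend on the church SD: at d = 0.2, power without versus with mediators is about 99% v 84% at SD 0.2, 91% v 66% at 0.3 and 84% v 57% at 0.4.

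**The case against.** The best defence is that the plan already separates the two questions. The sentence naming the arm comparison mentions no mediators. The SAP plans a run without covariates, Aim 2 tests arm against outcome on its own, and mediation has its own heading, methods and software. The only odds ratios promised from the mediator models are for mediators and moderators, not for condition, so those models may well be exploratory. All of this stands. A reader might infer that the SAP makes a mediator-adjusted model its primary analysis; the text does not go that far. But it also does not call those models exploratory or name any mediator-free comparison as primary, and Protocol 4i lacks the with/without sentence altogether.

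A reader might also infer that every listed mediator is measured after randomisation. The documents show this only for intervention exposure. Baseline values of the others, if those were meant, would be ordinary precision covariates.

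Finally, the figures above all rest on assumed mediator strengths, with equal shifts in one direction in the seven-mediator case. That is correct, and they should not be read as a forecast for this trial.

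**Conclusion.** The point holds as a gap that should be closed, not as a planned wrong analysis. The text puts potential mediators into the Aim 1 models, at least one of them can only be post-baseline, and no mediator-free model is protected as the primary result. Confidence in that reading is high.

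The size is unknown. Under the assumptions shown, an 18-point total effect would appear as anything from 16.7 down to 2.6 points with one mediator, or 16.5 down to 6.8 with seven. It would be unchanged with no mediation and little changed with weak mediation. Bias from mediator-outcome confounding is not included. It would go too far to conclude that the trial will lose a particular amount of effect or power.

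**What to change.** Add to SAP Aim 1 and to Protocol 4i:

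> The primary effect of TIPS is the odds ratio for condition at the survey 12 months after the pre-intervention baseline (Wave 1: baseline to the 12-month survey; Wave 2: baseline 2 to the survey labelled 18 months), from the random effects logistic regression with condition, the matched-pair and church terms, and baseline HIV testing. Any further covariate is a pre-specified baseline variable. No mediator, exposure measure or other post-baseline variable enters this model.

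The Wave 2 clause must be confirmed against Protocol 4a, which places baseline 2 at 6 months and the later surveys at 12 and 18 months; twelve months after baseline 2 is then the 18-month survey. The text should also say whether the pair term is fixed or random, since pairing is to be accounted for but no pair term is listed. It should say too what becomes of the individual-level random effect when there is one 12-month record per participant.

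Keep mediator models in Aim 2. Restrict the propensity analysis to baseline covariates, and label it and GEE supportive. Report the primary model without baseline testing as a sensitivity analysis.

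The cost is wording; no new data are needed. The real downside comes from baseline adjustment. Surveys are linked only through a code that participants create and must recreate (Protocol 4a and 11i), items may be skipped (Protocol 9e), and no match rate is given. One method for missing or unlinked baseline testing must therefore be stated in advance. The sensitivity model shows how much it matters.
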